**Protocol Date: 11/20/2024** 

### **Scientific Background**

Approximately two-thirds of American women are overweight or obese (OV/OB; BMIs > 25), and rates of obesity prior to pregnancy are increasing dramatically. For example, Kim and colleagues reported a 70% increase in the prevalence of pre-pregnancy obesity over a 10 year period. Rates of gestational diabetes mellitus (GDM), pre-pregnancy hypertension, and preeclampsia also have increased since 2000, and women who are OV/OB prior to pregnancy are at higher risk for preeclampsia, and gestational hypertension than are normal weight women. Prenatal OV/OB, along with weight gain in pregnancy, is related to difficult deliveries, an increased likelihood of macrosomia, congenital malformations, and obesity among the children born to OV/OB mothers.

Gestational weight gain (GWG) also affects maternal and child health independent of prepregnancy OV/OB. Excessive GWG robustly predicts the amount of postpartum weight retention, increases the risk of obstetric complications and is associated with adiposity among neonates, children, adolescents, and adults. The Institute of Medicine (IOM)reissued guidelines for GWG stratified by pre-pregnancy BMI that recommend GWG between 15 and 25 pounds for an overweight woman and 11 to 20 pounds for an obese woman. However, approximately 45% of women exceed IOM guidelines for GWG, and rates above 50% and as high as 63% have been reported. Moreover, women who begin pregnancy OV/OB are more likely to exceed IOM guidelines for GWG than are women with pregravid BMIs in the healthy weight range, and some evidence suggests that overweight women are even likelier than obese women to exceed GWG guidelines. Thus, although the causes of obesity are multi-factorial, the perinatal period is uniquely associated with women's obesity and offers a critical window for improving maternal health.

Perinatal interventions have not succeeded in decreasing GWG or affecting weight at one year postpartum.

Previous interventions to address perinatal weight have attempted either to minimize GWG or decrease postpartum weight retention. No intervention has successfully addressed the psychosocial and circumstantial changes that relate to maternal self-regulation across the transition from pregnancy through the postpartum year. Thus, the sequence of interventions that promotes behavior change from pregnancy through the postpartum period to improve weight at one year postpartum is unclear. We assert that the transition from pregnancy to postpartum offers a unique opportunity to optimize health by one year postpartum and that the optimal strategy of prenatal and postpartum interventions to effect maternal health may differ according to the amount of weight gained during pregnancy.

Interventions to address GWG have not helped OV/OB women avoid excessive GWG. A limited number of controlled studies have examined the efficacy of interventions to prevent excessive GWG. Overall efforts to moderate GWG have been unsuccessful or have been modestly successful, but only among subgroups of women. For example, Polley found intervention helped only women who were normal weight before pregnancy. Similarly, Phelan et al tested the efficacy of a lifestyle intervention to decrease the number of women with excessive GWG. In a sample of 401 women, a lifestyle intervention that addressed eating and activity and included provision of body weight scales and pedometers succeeded in minimizing GWG only with women who were normal weight prior to pregnancy. Thus, it appears interventions may succeed

in preventing excessive GWG, but not among women who begin pregnancy OV/OB.

Additionally, with the exception of a lifestyle program delivered by nurses in Finnish clinics, previous interventions to prevent excessive GWG have been limited in intensity. Interventions have been designed to offer a small number of group-based sessions, improve GWG monitoring among obstetricians, or provide dietary advice without teaching the behavioral principles necessary for longer-term behavior change. To optimize longer-term maternal weight and health for women who begin pregnancy overweight, addressing GWG alone may be insufficient, particularly through brief contacts. Additional components, intensified interventions or an approach to weight over the perinatal period may be necessary to alter longer-term obesity-related risks, particularly among OV/OB women.

Interventions to promote postpartum weight loss have not succeeded among lower income women. A second approach to perinatal weight management has focused on postpartum weight loss and specifically on the prevention of GWG retention. Substantial evidence indicates that changes to eating or activity postpartum pose minimal, if any, risk for OV/OB postpartum women. Studies examining the effects of diet and exercise on lactation have documented that lifestyle changes do not adversely affect breast milk composition, production or quality or infant growth and development although OV/OB women may have difficulty initiating or sustaining breast feeding. Thus, the potential risks of postpartum weight loss for OV/OB women are minimal and offset by potential benefits.

However, in contrast to interventions for GWG, postpartum weight management efforts have been modestly successful. Randomized controlled trials for postpartum weight loss have tested the efficacy of brief group sessions, mailed correspondence and group sessions coupled with individualized phone calls. For example, Ostbye assigned women to an eating and exercise intervention or a no treatment control at 6 weeks postpartum and followed women for one year. Intervention comprised 18 group classes addressing exercise and eating and 6 individualized telephone contacts. Enrollment in the program was readily accomplished and retention rates during the postpartum year were excellent, suggesting that OV/OB women are interested in postpartum weight management. However, intervention was not associated with weight loss at one year. Moreover, attendance at group classes, which predicted weight change, was very low (3.8 of 18 classes) and younger, African American and lower income women were less likely than older, white, higher income women to participate. Intervention also was delivered irrespective of GWG, and questions about the need for additional intervention for women who met or failed to meet GWG guidelines remain.

Finally, the limited efficacy of postpartum weight loss interventions may be due to timing. Most trials have initiated intervention 6- or 12-months after childbirth, and one recruited women at 6-weeks postpartum. In summary, previous postpartum weight loss efforts, and our work on health behavior change postpartum suggests that, to maximize efficacy, postpartum interventions need to engage women from lower socioeconomic groups, be delivered in a fashion that addresses postpartum stressors and capitalize on the immediate transition between pregnancy and the early postpartum period.

The proposed SMART is innovative as the first effort to evaluate different combinations, or

sequences, of intervention across pregnancy and the postpartum period to decrease maternal weight and improve health by one year postpartum. Use of a SMART design provides the opportunity to test the efficacy of different sequences of intervention during pregnancy, postpartum or both, and to collect data on the benefit of adapting this sequence according to GWG. SMART and other dynamic treatment approaches have been applied to psychiatric and health, conditions including drug use, and adult and child weight loss, but this proposal represents the first use of SMART for perinatal weight. Although pregnancy has been called a critical period for weight management, there are no data to determine if delivering a lifestyle intervention prenatally, postpartum or across the perinatal transition optimizes maternal weight and health by one year postpartum.

Moreover, the transition from pregnancy to postpartum provides an ideal period to evaluate the utility of GWG as a potential tailoring variable. GWG is routinely documented and easily measured in all women. As such GWG would be a pragmatic variable on which to tailor treatment sequences. However, there are no data on the efficacy of GWG as a tailoring variable for perinatal weight interventions. The proposed SMART design enables us to evaluate the optimal sequence and to test the efficacy of different strategies, or combinations of sequences, for women who do and do not meet GWG goals. For example, we will compare the strategy of starting with HABITpreg and continuing with HABITpost only when GWG exceeds IOM guideline to the strategy of no treatment postpartum for women who receive HABITpreg and met their GWG goal. Alternatively, maternal weight one year postpartum may be decreased most by starting with TAU and receiving HABITpost only if GWG is high. Finally, by stratifying women according to pregravid BMI, we will be in a unique position to explore whether a different decision rule is more efficacious for a particular weight group.

There is substantial innovation in using interventions to address the different situational and psychosocial needs of women during pregnancy and the postpartum year. To date, no interventions have successfully addressed the unique sequential challenges presented by the perinatal period. We have made adaptations to the content and modality of the lifestyle interventions described, HABITpreg and HABITpost, that address conceptually relevant and modifiable factors that affect health in either pregnancy or the postpartum period. In HABITpreg, designed to address excessive GWG, we include a focus on weight stability given that weight gain is expected. In HABITpost, we recognize the increased time demands of infant care and include a focus on postpartum sleep given the impact of sleep on mood and weight in general and postpartum weight specifically, as well as the use of telephone and home visits as in our previous postpartum work.

A final innovative aspect of the proposed research is the diversity of the proposed sample. Previous work on perinatal weight management with women from minority groups or with lower incomes has been limited. Although rates of obesity prior to pregnancy have increased among women from all backgrounds, African American women had the highest prevalence of obesity in a recent survey, and the relationship between parity and weight gain is particularly strong among African American women. Lower levels of education also are associated with greater weight retention postpartum. Given our previous perinatal health behavior research, we are uniquely situated to recruit and retain women of diverse backgrounds and to address questions about the optimal sequence of weight-related interventions for women from minority groups and of lower socioeconomic status, who may benefit most.

## **Study Objectives**

The purpose of this study is to determine the best combination of lifestyle intervention to improve maternal weight, health and psychological symptoms at 1 year postpartum.

Specific Aim 1: Determine the combination of prenatal and postpartum lifestyle interventions that optimizes maternal weight, cardiometabolic health, depressive symptoms and stress at 12-months postpartum.

Hypothesis 1: Women in HABITpreg who are assigned to HABITpost will have improved weight and secondary outcomes at 12-months postpartum relative to women who receive only HABITpreg or only HABITpost.

Hypothesis 2: Women who receive only HABITpost will have improved weight and secondary outcomes at 12-months postpartum compared to those who receive only HABITpreg or only TAUpost.

Specific Aim 2: Determine the optimal combination of interventions based on GWG that improves weight, cardiometabolic health, depressive symptoms and stress at 12-months postpartum.

Hypothesis 3: Among women who receive HABITpreg or TAUpreg and gain excessive GWG, those who are assigned to HABITpost will have improved weight and secondary outcomes at 12-months postpartum compared to those in TAUpost.

Hypothesis 4: Among women who receive HABITpost, women who met GWG goals will have improved weight and secondary outcomes compared to those who exceed GWG goals regardless of prenatal assignment.

Exploratory Aims: Evaluate the optimal sequence of interventions by prenatal weight. We will determine, for example, if the strategy of HABITpreg then HABITpost, regardless of GWG, optimizes outcomes for obese women, and if TAUpreg then HABITpost is helpful for overweight women only when GWG is excessive. Evaluate the effect of the sequence of interventions on infant risk for obesity.

Impact: This SMART is designed to identify the sequence of interventions most likely to improve maternal health at one year postpartum. Optimizing the sequence of behavioral interventions to address specific needs during pregnancy and the first postpartum year can maximize intervention potency and mitigate longer-term cardiometabolic health risks for women and their children.

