#### assessment.

Blood draw. Participants will be asked to provide a blood sample to measure glucose/insulin/insulin resistance and lipids/inflammation. Levels of estrogen and progesterone will also be measured. To gather this information, up to about 2-3tb of blood will be collected by a qualified individual contracted through the Magee CTRC. This will be done at all of the assessments. If women are unable to attend their assessment at Magee CTRC we will send a trained phlebotomist to their home to complete the blood draw.

Infant data: We will conduct medical chart reviews to obtain infant height, weight, and medical history during their first year of life, in accordance with the study procedures for participating women. We will also collect data on the infant gut microbiome using stool sample kits in accordance with procedures from the Center for Medicine and the Microbiome (CMM). At their 2-6 week postpartum visit, mothers will be provided with fecal sample collection kits and instructed to collect infant fecal samples, then mail them in pre-paid approved envelopes to the CMM. We will ask participants to complete 4 subscales of the Infant Behavior Questionnaire Revised (IBQ-R) at T12. This survey is designed to measure temperament in infants.

Safety alerts: We will ask participants at each follow-up (T1, T6 and & T12) about any medical events occurring between visits. Individuals enrolled in the ancillary study will also answer these questions at their T2 visit. Any medical events discussed will be logged on an interview form labeled with the participant's ID number.

COVID-19 Information: We will ask participants about any COVID-19 positive tests they had while they were in the study. Additionally, they will be asked if they received the COVID-19 vaccine. This interview form will be completed at their final assessment timepoint (12 months postpartum).

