There are 8 sequences or combinations of intervention in this SMART, which we use to define group for hypothesis testing. Time also is a generic factor, and the number of levels will depend on the outcome being modeled. For example, for weight, mood and stress, time will be a linear term beginning at baseline, and a quadratic term will be added to the model if necessary. For other outcomes, time will be a factor with 4 levels (baseline, end of pregnancy, and 6- and 12-months postpartum). We also will evaluate the need to control for the effects of potential confounds such as race, age, socioeconomic status (fixed covariates) as well as breastfeeding, smoking status and physical activity (time-varying covariates). If the coefficients for groups or group by time interactions are significant, planned contrasts will evaluate groups on weight and related outcomes at 6- and 12-months postpartum. Additionally, we will create a binary variable for 5% weight loss and use generalized mixed-effect models with the logit link to compare groups on proportions with 5% loss at 6- and 12-months postpartum.

Finally, to fully utilize a SMART design, and to evaluate the utility of using GWG as a tailoring variable, we will explore what the optimal strategy is and for which participants. A dynamic strategy is a decision rule about which intervention is best initially and what intervention follows, depending on the response status. The proposed deisgn produces HABITpreg and TAU during pregnancy, and women who do and do not meet IOM guidelines for GWG each have HABITpost and TAU postpartum, resulting in the 8 possibilities sequences.

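### H1-H4 claim improvement in secondary outcomes whose measures are not fixed and which have no rule across outcomes, so a secondary claim can rest on one nominally significant marker

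*Combined protocol and SAP*

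**What the plan says.** In the combined protocol and SAP, under Study Objectives, Aim 1 seeks the combination that "optimizes maternal weight, cardiometabolic health, depressive symptoms and stress at 12-months postpartum", and Aim 2 covers the same four areas. All four hypotheses carry the same double claim:

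- H1: women given both interventions "will have improved weight and secondary outcomes at 12-months postpartum relative to women who receive only HABITpreg or only HABITpost".
- H2: women given only the postpartum intervention will have "improved weight and secondary outcomes at 12-months postpartum compared to those who receive only HABITpreg or only TAUpost".
- H3: among women with excessive gestational weight gain (GWG), "those who are assigned to HABITpost will have improved weight and secondary outcomes at 12-months postpartum compared to those in TAUpost".
- H4: among women given the postpartum intervention, "women who met GWG goals will have improved weight and secondary outcomes compared to those who exceed GWG goals regardless of prenatal assignment".

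Only the aims on prenatal weight group and on infant obesity risk are headed exploratory.

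The candidate measures appear in Study Design & Methods. Blood is drawn to "measure glucose/insulin/insulin resistance and lipids/inflammation", with no lipid fraction or inflammation marker named. Waist circumference is also taken. Depressive symptoms are measured by both the CES-D and the EPDS, and stress by the PSS.

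Under Statistical Considerations, mixed models are fitted with an eight-level group factor. If the group or the group-by-time term is significant, "planned contrasts will evaluate groups on weight and related outcomes at 6- and 12-months postpartum". That section gives no significance level, no order among the secondary outcomes and no adjustment across them.

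**The concern.** The secondary claims sit inside the stated hypotheses, not in a separate exploratory section, yet their content is open. Followed as written, a statement that an intervention improves cardiometabolic health could rest on whichever blood marker reached nominal significance. A statement on depressive symptoms could rest on whichever of two scales did. The outcomes may also favour different combinations, one on weight and another on stress, and nothing says which result answers Aim 1. This problem concerns the number of outcomes. Settling the number of group contrasts on weight would not resolve it.

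**Working it through.** The documents state no alpha, error rate or sample size, so there is no figure of the plan's own to reproduce. The rates below are illustrations under stated assumptions.

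**Inputs from the documents.** There are three secondary domains and eight groups (prenatal arm × GWG status × postpartum arm). H1 and H2 give two contrasts each, read here as both interventions against each one alone, and postpartum only against prenatal only and against usual care throughout. The hypotheses' time point is 12 months (H4 gives none).

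**Number of measures, k.** One per domain gives k = 3. The five kinds of blood measure alone give k = 5. Waist, five blood measures, CES-D, EPDS and PSS give 1 + 5 + 2 + 1 = 9. I use k = 10 as an upper illustration, since lipids and inflammation may each yield more than one marker.

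**Assumptions.** Two-sided 0.05 per test, no true effects, equal correlation ρ between outcomes from 0 to 0.8.

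**Step 1: one contrast, no gate.** This isolates multiplicity across outcomes. With ρ = 0 the rate is 1 − 0.95^k:

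- k = 3: 1 − 0.857 = 14.3%
- k = 5: 1 − 0.774 = 22.6%
- k = 10: 1 − 0.599 = 40.1%

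With correlated outcomes, each test statistic is written as √ρ·U + √(1−ρ)·V_j, with U and V_j independent standard normals, and the rate is P(at least one |T_j| > 1.96). By simulation, ρ = 0.5 gives about 18% for k = 5 and 28-29% for k = 10. With ρ = 0.8 the rates are about 10%, 13% and 17% for k = 3, 5 and 10.

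**Step 2: four H1/H2 contrasts behind the gate.** I simulated eight equal cells per outcome. A false positive is counted only if that outcome's 7-df group test is significant at 0.05 and at least one of the four contrasts has |T| > 1.96.

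| Measures | One contrast, ungated (ρ = 0.8 to 0) | Four contrasts, group-test gate (ρ = 0.8 to 0) |
|---|---|---|
| 3 | 10-14% | 6-9% |
| 5 | 13-23% | 9-14% |
| 10 | 17-40% | 12-26% |

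**Step 3: what the gate does.** At ρ = 0.5, the four contrasts without any gate give about 61% for 8 measures and 66% for 10. With the group-test gate these fall to about 17% and 20%. The gate helps substantially but does not reach 5%.

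**Step 4: what raises the gated rates.** The plan's gate opens on either of two terms, and there are four hypotheses. With an either-term gate, six contrasts (H1-H4, H3 pooled) and ρ from 0 to 0.5, the 12-month rates are 10-13% for 3 measures, 16-21% for 5 and 25-34% for 9. Adding 6 months (9 measures, ρ = 0.3, time as a factor) raises the rate from about 32% to 40%. The groups also include GWG status, so GWG-related differences could open the gate for some outcomes with no treatment effect.

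**Step 5: direction.** These are two-sided rates and include apparent harm. In the Step 4 setting, false findings of improvement alone come to 10-13% for 5 measures (against 16-21%) and 15-22% for 9 (against 25-34%).

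**The case against.** The best defence is that the plan has more structure than this point suggests. Weight is named apart from the secondary outcomes in every hypothesis, which is a one-step ranking. Three domains are listed. Stress has a single scale, and the protocol gives a reason for choosing the CES-D. The hypotheses can be read as requiring improvement in weight and in the secondary outcomes together, so one stray marker would not support them. Many trials also leave secondary outcomes unadjusted and rely on labelling.

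Much of this stands. A reader might infer that the plan has no hierarchy at all; it does set weight apart, and the gap lies among and within the secondary domains, most clearly the cardiometabolic one. Counting glucose, insulin and insulin resistance as three outcomes is also a reading of a slash-separated list. A reader might infer that the gate gives no protection across outcomes; Step 3 shows that it does.

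A reader might also take a rate near two-thirds as the plan's error rate or its ceiling. The documents support neither. About 66% needs 10 measures, four contrasts, ρ = 0.5 and every outcome's gate open, and it mixes the number of contrasts with the number of outcomes. With the gate open for 5 of the 10 outcomes it is about 51%, and for 3 about 42%. With all gates open, ρ = 0.8 gives 45%, while nine measures and six contrasts give 77-89% for ρ from 0 to 0.5.

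What does not stand is that the plan's wording closes the gap. It nowhere says that weight must succeed first, that the hypotheses are conjunctive, or that secondary results are exploratory. The analysis evaluates weight and related outcomes by the same contrasts.

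**Conclusion.** The point holds in a limited form. The secondary measures behind H1-H4 are not fixed, and no ordering, adjustment or label governs them. Under two-sided 0.05, no true effects and correlations of 0 to 0.8, the chance of at least one false-positive secondary result exceeds 5% in every setting tabulated, from about 6% (3 measures, gated) to about 40% (10 measures, one ungated contrast). The spread reflects what the plan leaves unstated: alpha, the list of measures and their correlation. No single figure in that range should be quoted as the trial's error rate. The analysis of weight itself is untouched by this point. It is a cheap improvement that determines which secondary statements the trial may make.

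**What to change.** State under Study Objectives and again under Statistical Considerations that 12-month weight alone decides H1-H4. State that the secondary outcomes are reported as estimates with 95% confidence intervals, labelled exploratory, and that no hypothesis is declared supported on them.

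This takes a few sentences and needs no new data or visits. The cost is fewer claimable secondary findings. A confirmatory secondary claim would need more: one named measure per domain, a stated alpha, a definition of success on weight where a hypothesis has two contrasts, and control across contrasts as well as outcomes. Holm adjustment over three measures within each contrast would not be enough. If weight truly responds and the secondaries do not, four such contrasts still leave about a 15-16% chance of a false secondary claim.

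### Hypothesis 4 compares GWG groups who all receive HABITpost, so for weight it mixes prognosis with moderation; no numbered hypothesis or named contrast compares HABITpost with TAUpost in women who did not exceed the goal

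*Combined protocol and SAP*

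**What the plan says.** Study Objectives places two numbered hypotheses under Aim 2. H3 compares HABITpost with TAUpost among women whose GWG was excessive. H4 states "Among women who receive HABITpost, women who met GWG goals will have improved weight and secondary outcomes compared to those who exceed GWG goals", whatever the prenatal assignment. H1 and H2, under Aim 1, are not split by GWG.

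Scientific Background says "Excessive GWG robustly predicts the amount of postpartum weight retention". It also promises "to test the efficacy of different strategies, or combinations of sequences, for women who do and do not meet GWG goals". Its worked comparison, for women who start with HABITpreg, contrasts two postpartum options: "HABITpost only when GWG exceeds IOM guideline to the strategy of no treatment postpartum for women who receive HABITpreg and met their GWG goal". Its other example is "starting with TAU and receiving HABITpost only if GWG is high". Women who met the goal receive no HABITpost in any of these.

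Two exploratory examples in Study Objectives come closer. One asks "if the strategy of HABITpreg then HABITpost, regardless of GWG, optimizes outcomes for obese women". The other asks whether TAUpreg followed by HABITpost helps overweight women solely in the case of excessive gain.

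Statistical Considerations defines eight groups (prenatal arm by GWG status by postpartum arm). It runs contrasts at 6 and 12 months if group or group-by-time coefficients are significant, and leaves the use of GWG for tailoring to exploration. It does not list the contrasts. The Intervention section re-randomises every participant after T1.

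**The concern.** A rule that makes postpartum treatment depend on GWG needs the effect of HABITpost against TAUpost in each GWG group. H3 supplies it for exceeders. H4 varies GWG and holds treatment fixed, so it supplies no treatment effect at all. Because the protocol itself says excessive gain predicts weight retention, a weight difference in H4's direction is plausible before any treatment is given.

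Both numbered Aim 2 hypotheses could then be reported in full with no randomised estimate for women who stayed within the guideline, which is half of the tailoring question. A confirmed H4 would also be easy to misread as evidence about tailoring.

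**Working it through.** The documents give no sample size, SD or effect size, so there is no planned figure to reproduce. The algebra needs none.

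**Algebra.** Write mean 12-month weight as b0 + bP·HABITpost + bG·Exceed + bPG·HABITpost·Exceed.

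- H4 (exceeded minus met, all on HABITpost) = bG + bPG
- H3 (HABITpost minus TAUpost, exceeders) = bP + bPG
- HABITpost minus TAUpost, women who did not exceed = bP
- Moderation = (bP + bPG) − bP = bPG

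Of the 2 × 2 × 2 = 8 groups, H3 uses the four exceeder groups and H4 the four HABITpost groups. The two groups of met-goal women on TAUpost are in neither. Two equations in three unknowns do not identify bP or bPG.

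**Numbers (assumed).** Suppose exceeders gain 10 to 20 lb more and 20% to 60% of that remains at 12 months. Then bG runs from 10 × 0.2 = 2 lb to 20 × 0.6 = 12 lb. The table takes the 15 lb gap: bG = 3, 6 or 9 lb at 20%, 40% or 60%. A positive H4 favours met-goal women; a negative treatment effect favours HABITpost.

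| Case | bG | bP | bPG | H4 | H3 | Effect if not exceeded |
|---|---|---|---|---|---|---|
| Inert | 6 | 0 | 0 | +6 | 0 | 0 |
| Helps all by 3 lb | 6 | −3 | 0 | +6 | −3 | −3 |
| Helps exceeders only | 9 | 0 | −3 | +6 | −3 | 0 |
| Helps exceeders only, weaker prognosis | 3 | 0 | −3 | 0 | −3 | 0 |

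Rows 1 and 2 show that a benefit shared by all leaves H4 unchanged. Rows 2 and 3 give identical H3 and H4 results with opposite answers on tailoring. In row 4, H4 shows no difference although benefit depends on GWG.

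**Scale.** The plan does not say whether the 12-month contrast is on weight level or on change from T0, and this matters. A simulation assumed 0.3 kg of 12-month weight per kg of GWG, GWG SD 6 kg, prepregnancy weight 74 (SD 7) kg in overweight and 97 (SD 16) kg in obese women, and 15% of GWG gained before T0. With inert HABITpost the mean H4 gap was 1.4 kg on change from T0 and 2.9 kg on level. With an assumed within-stratum correlation of −0.2 between prepregnancy weight and GWG, the level gap became −0.9 kg. So the size of H4 with no treatment effect, and on the level scale even its sign, depends on prognosis and scale.

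In the same simulation, with 200 women, H4 was significant in its own direction in 17% (change) and 16% (level) of trials. These are illustrations only and ignore the significance condition on contrasts. Adding a single-time-point version of that condition cut both to about 7%.

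**Precision of the missing contrasts.** Assume an SD of 7 kg, half the women in each BMI stratum, and equal postpartum arms. Scientific Background gives "approximately 45% of women exceed IOM guidelines for GWG, and rates above 50% and as high as 63% have been reported" and adds that "some evidence suggests that overweight women are even likelier than obese women to exceed GWG guidelines". Assigning 63% to overweight and 45% to obese women is my assumption; the average is (63 + 45)/2 = 54%. With 200 women that is 54 exceeders and 46 others per arm.

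- Exceeders: 1.96 × 7 × √(2/54) = 2.6 kg half-width
- Not exceeded: 1.96 × 7 × √(2/46) = 2.9 kg
- Moderation: 1.96 × 7 × √(2/54 + 2/46) = 3.9 kg

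The moderation half-width falls to 3.2 kg with 300 women and 2.8 kg with 400. Simulated power to detect a 3 kg benefit confined to exceeders is 33%, 46% and 58% at 200, 300 and 400 women; for 5 kg it is 71%, 87% and 95%.

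**The case against.** The best defence is that nothing is missing from the design. Every woman is re-randomised, the eight-group model contains both met-goal postpartum arms, and Scientific Background promises comparisons for women who do and do not meet their goals. The plan names no contrasts for any hypothesis, so one more unnamed contrast is hardly distinctive. The exploratory question about overweight TAUpreg women also cannot be answered without comparing HABITpost with TAUpost in women who did not exceed. And H4 is not worded as a test of moderation.

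Much of this stands. A reader might infer that the trial cannot estimate the effect in met-goal women, or that the plan never touches the question; the documents support neither. Nor does any section say that H4 alone will decide who is offered HABITpost.

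What remains is narrower. The exploratory example implies the comparison for one BMI group and one prenatal arm without defining it. The general contrasts depend on an overall test. GWG status is part of the group definition, so prognosis alone could make that test significant, and a non-significant test would suppress the contrasts. H1 to H3 at least name the groups to be compared; no hypothesis does so for HABITpost against TAUpost in women who did not exceed.

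**Conclusion.** The concern holds for weight, as a gap in prespecification and in what H4 can show. H4 estimates bG + bPG, and H3 and H4 together identify neither the HABITpost effect in women who did not exceed nor its dependence on GWG. This follows from the hypotheses as written and needs no assumed number. The 2 to 12 lb range and the rejection percentages rest on assumed inputs. They should not be read as error rates of the planned mixed-model analysis.

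A reader might extend the point to depressive symptoms and stress. The protocol makes no matching statement that GWG predicts those outcomes, so the prognosis argument is not supported there. The data needed are already being collected, so the gap can be closed before analysis and is worth closing.

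**What to change.** For Aim 2, prespecify:

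- the HABITpost-minus-TAUpost difference in 12-month weight, with its 95% confidence interval, in each GWG stratum (exceeded / not exceeded);
- the difference between those two as the named moderation contrast;
- adjustment for prenatal arm, prepregnancy BMI stratum and T0 weight;
- reporting of all three whether or not the overall group test is significant;
- whether weight contrasts are on 12-month level or on change from T0.

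Use the yes/no definition of excessive GWG in Study Design & Methods, and state that not exceeded includes women below the lower IOM limit (15 lb for overweight, 11 lb for obese women). Keep H4, labelled descriptive or prognostic.

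State the timing as well. GWG uses the last weight before delivery, so it is completed after re-randomisation at T1 but before HABITpost starts at delivery. Late gain could in principle follow knowledge of the assignment, so repeat the analysis with GWG classified from weight at or before T1 as a sensitivity check.

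The cost is wording: one hypothesis relabelled and three estimates named, from groups already in the model. The drawback is precision. With equal groups and a common SD, the moderation contrast has √2 = 1.41 times the standard error of H4. Emphasis should fall on the two stratum estimates and their intervals, and a null interaction must not be read as equal benefit.
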